#### 8.1.3 PROFILING MICROBIAL COMMUNITY FUNCTION

After total RNA extraction and rRNA depletion (RiboZero Gold Kit, Illumina, San Diego, Ca, or equivalent), libraries will be constructed and Illumina-based sequencing will be performed to generate ~30 million 2x150bp paired end reads per sample (our rarefaction analyses have previously shown such sequencing depth is sufficient to identify the vast majority of species and enzymes present in the samples[75]). Reads will be processed for quality and contaminants using established pipelines (e.g. [66, 68, 104]). Reads will be assembled using appropriate state of the art tools such as SPAdes[105] and subsequently annotated with taxonomic and functional assignments Expression will be normalized to Reads per Kilobase of transcript per million mapped reads. Annotations are mapped onto biochemical pathways and complexes such as those defined by the Kyoto Encyclopedia of Genes and Genomes [104]. The output of these analyses are readouts of microbial gene expression detailing biochemical activities as well as the taxa responsible.

#### 8.1.4 PROFILING OF PATIENT AND MICROBIOME METABOLITES AND INFLAMMATORY MARKERS

To gain more mechanistic insights into the relationship between microbiome function and maternal health and birth outcomes, we will deploy metatranscriptomics, metabolomics and markers of inflammation.

We will obtain host readouts that reflect gut health and pathogen challenge, by examining markers in the stool for Calprotectin, Lipocalin and Claudin 15. These markers will be examined

in the maternal stool samples collected during the 2 pregnancy visits (MV1 and MV2) for 200 of the participants. We will target this analysis at the 200 participants representing the two extremes of weight gain; the 100 participants with the highest and 100 participants with the lowest WHZ scores.

Stool samples will be sent from SickKids to The Metabolomics Innovation Centre (TMIC) for analysis of general metabolites (e.g. SCFAs, amino acids, intermediates in glycolysis and nucleotide metabolism, among other metabolites), using the TMIC Prime Metabolomics platform[105]. This analysis will be targeted at the maternal stool samples collected during pregnancy (MV1 and MV2); with a focus on the 200 participants at the two extremes of weight gain: the 100 participants with the highest and 100 participants with the lowest WHZ scores.

Blood samples will be analyzed at AKU for Hemoglobin + MCV, Ferritin, and CRP. Blood samples will be shipped on dry ice to SickKids and then to the TMIC Centre, where they will be analyzed for Metallomics using the TMIC Metallomics platform[106]. The output of these analyses will be concentrations of metabolites that are expected to correlate with pathway expression data. Blood samples will be biobanked at SickKids.

Blood proteomics will allow for a deeper investigation into the relationship between the maternal microbiome and maternal weight gain and the effects on offspring. Proteomics will be conducted at the Sickkids SPARC (Sickkids Proteomics, Analytics, Robotics and Chemical Biology Centre)[107]

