### 3 STUDY OBJECTIVES

**Table 4: Study Objectives**

OBJECTIVES	ENDPOINTS	JUSTIFICATION FOR ENDPOINTS
Primary		
To assess if alterations of the microbiota in the maternal gut (dysbiosis) is associated with maternal gestational weight gain.	The primary endpoint will be maternal gestational weight gain (GWG) during pregnancy, measured between the first (10-14 weeks post-conception) and second time point (30-34 weeks post conception).  To monitor microbiome dynamics, 16S and 18S rDNA surveys will be	Weight gain is a key predictor of adverse birth outcomes[83, 84].

OBJECTIVES	ENDPOINTS	JUSTIFICATION FOR ENDPOINTS
	
applied to the maternal stool samples to monitor the bacterial and eukaryotic components of the microbiome.
	
To determine the association between maternal microbiome dysbiosis during pregnancy and birth outcomes, infant growth, nutritional status and health status in the first year of life.	
The specific birth outcomes evaluated will include preterm birth, birth weight, SGA, LGA, head circumference at birth, mortality, morbidity.
 
The specific infant outcomes evaluated will include the following growth and nutritional status parameters; WHO z-scores for weight, length, head circumference and MUAC during the first year.
 
Birth characteristics will be collected, including information on vaginal or cesarean birth (elective, emergency), placental insufficiency and antibiotic usage.
 
Infant morbidity and mortality will be assessed at follow-up visits, with questions regarding care-seeking, hospitalizations and treatments for any morbidity; including antibiotic usage.
 
For the infants an assessment of amount and mode of feeding will be obtained at 3-months, 6-months and 12-months.
 
To monitor microbiome dynamics, 16S and 18S rDNA surveys will be applied to the maternal stool samples to monitor the bacterial and eukaryotic components of the microbiome.
	
This will allow for an examination of the association between the maternal microbiome and birth outcomes.

Secondary		
To link the maternal microbiome to dietary intake, with a focus on calories and macronutrients.	
The maternal participants will complete a 24 hour dietary recall at both time points during pregnancy and at 1-year post-partum.
	
Quantitative measures of nutritional status will provide parameters to better inform microbiome analyses.

OBJECTIVES	ENDPOINTS	JUSTIFICATION FOR ENDPOINTS

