## 9 STATISTICAL CONSIDERATIONS

### 9.1 POWER CALCULATION

The adequacy of the sample size was verified using the ‘pwr’ package (version 1.2-2) in R (version 3.6.1). Calculations were based on the correlation between  $\alpha$ -diversity (Shannon index) and weight gain during pregnancy. Assuming 400 participants are recruited into the study, and a type I error rate of 0.05, there will be 80% power to detect a correlation coefficient ( $r$ )  $>0.14$ . This is conventionally considered a small effect size[109]. Thus, we expect to be powered to reveal significant association between weight gain during pregnancy and diversity. Further, a study of 123 lean and 24 obese individuals, revealed 96% power to detect differences in Bacteroidetes abundance and 80% power for Firmicutes[110], while a cohort of 44 Malawian malnourished children was sufficient to detect significant differences in bacterial  $\alpha$ -diversity in the presence and absence of *Blastocystis*.

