##### **Microbiome Variables**

1. Maternal gut bacteria profile
2. Maternal eukaryotic microbe profile
3. Infant gut bacteria profile
4. Infant eukaryotic microbe profile
5. Maternal metabolomic profile of stool
6. Maternal metabolic pathway expression profile
7. Maternal bacterial gene expression profile

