To complement these analyses, we will also undertake an integrative modeling strategy based on Similarity Network Fusion framework[112] to analyze the contribution of each variable (clinical, microbiome and gender-related) on gestational weight gain. In this approach we construct a series of networks (one for each variable) in which nodes represent patients and links represent similarities between patients (e.g. based on correlations between e.g. microbiome or metabolite profiles). Networks are then fused using a method based on message-passing theory to identify links shared between patients supported by multiple datatypes, eliminating poorly supported links and strengthening links supported by multiple datatypes. This allows the integration of all available datasets to uncover their global substructures that can be associated with gestational weight gain. In an alternative approach, we will also employ Random Forests to identify

combinations of variables (clinical, microbiome and gender-based; Table 8) that correlate with gestational weight gain.

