#### 9.4.2 ADDRESSING THE SECONDARY OBJECTIVES

This study has the following secondary objectives: 1) To link the maternal microbiome to dietary intake, with a focus on calories and macronutrients; 2) To integrate maternal anthropometric factors, morbidity and mortality with microbiome data to reveal key modulators (microbial taxa and metabolites) of dietary intake during pregnancy and the post-partum period; 3) To determine the impact of the maternal microbiome during pregnancy, including the exposure to pathogens and parasites, on the development of the infant microbiome; and 4) To investigate the maternal microbiome's exposure to pathogens and parasites, and the association with intestinal inflammation.

To assess these secondary objectives, we will employ general linear models. In a first approach we will perform PERMANOVA and probe the association of microbial community structure with the clinical variables. Pair-wise differences in microbiome structure between patient samples at similar time-points are defined by abundance-weighted pair-wise differences using the Bray-Curtis dissimilarity metric. DESeq2, a method for differential analysis of count data, will subsequently be applied to investigate both associations of specific taxa with the clinical variables, together with the strength of those associations. DESeq2 will utilize default settings, and q-values calculated with the Benjamini-Hochberg procedure to correct p-values while controlling for false-discovery rates. These analyses will reveal which clinical variables (including exposure to pathogens and parasites) correlate with the maternal microbiome from a taxonomic perspective.

To probe the association of clinical variables with the function of the microbiome, PERMANOVA and DESeq2 analyses will be performed replacing microbial community structure metrics with microbial community function metrics, specifically: 1) metatranscriptomic profiles; and 2) stool metabolomic profiles. Profile differences will be defined through Spearman rank differences for metatranscriptomic data and Euclidean distance metrics for metabolomic profiles. These analyses will reveal microbial genes, metabolites and pathways that correlate with clinical variables.

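### Stool inflammation markers, and mainly stool metabolomics, come from 200 mothers picked at the extremes of weight gain, but enter the weight-gain models and secondary objective 4 with no restriction or correction for that selection

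*Protocol*

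**What the plan says.** - **Who is assayed.** Section 8.1.4 restricts the three stool markers at MV1 and MV2 to 200 mothers: "We will target this analysis at the 200 participants representing the two extremes of weight gain", defined as "the 100 participants with the highest and 100 participants with the lowest WHZ scores". The sample-type table in section 8 agrees, with 200 mothers at two visits. Stool metabolomics is described as focused on the same 200.
- **What weight gain is.** Table 4 (Study Objectives): "The primary endpoint will be maternal gestational weight gain (GWG) during pregnancy", taken from MV1 to MV2.
- **Where the assays are used.**
  - Table 8 lists maternal inflammation markers among the clinical variables and "Maternal metabolomic profile of stool" among the microbiome variables. Neither carries a note that it exists for only part of the cohort.
  - Section 9.4.1 applies Similarity Network Fusion "to analyze the contribution of each variable (clinical, microbiome and gender-related) on gestational weight gain", and Random Forests on the Table 8 variables.
  - Section 9.4.2 gives secondary objective 4 as "To investigate the maternal microbiome's exposure to pathogens and parasites, and the association with intestinal inflammation". Its row in Table 4 makes stool markers the endpoint, with no mention of the 200.
  - Section 9.4.2 also carries stool metabolomic profiles into its PERMANOVA and DESeq2 analyses.
- **What is disclosed.** Table 4 says the assays are used selectively, but only under the first exploratory objective. The protocol nowhere says that these analyses are confined to the 200, how selection is allowed for, or how the other 200 women enter.

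**The concern.** Sampling the two tails is an efficient way to compare high and low gainers. The difficulty lies in the other uses of the same data.

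First, whether a marker value exists is decided by the outcome of the GWG models. Analysing only women with values stretches the spread of GWG and enlarges correlations with it. The section 9.4.1 models are meant to show what each variable contributes, so inputs from the tails would be compared with 16S and 18S profiles measured in all women on unequal terms. Naive filling of the gaps has its own problem in a tree model, because the filled pattern can itself signal a middling weight gain.

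Second, the central hypothesis in section 4.1 makes weight gain a consequence of dysbiosis, exacerbated by nutritional status or pathogen exposure, through impaired absorption. If pathogen load and intestinal inflammation both relate to GWG, choosing women by GWG can create or alter an association between them. Objective 4 would then not describe the recruited women.

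**Working it through.** **Inputs.** N = 400, alpha = 0.05 and 80% power from section 9.1 (two-sided assumed); 100 highest plus 100 lowest from section 8.1.4. Assumed here: GWG is normal, ranking is on GWG itself, all 400 women are available, and relations are linear. The correlations below are illustrative, because the protocol gives none for these assays.

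**1. The plan's own figure.** Section 9.1 states: "Assuming 400 participants are recruited into the study, and a type I error rate of 0.05, there will be 80% power", for r above 0.14 between the Shannon index and weight gain. By Fisher's z, r = tanh[(1.960 + 0.842)/√397] = tanh(0.1406) = 0.140. The method of the pwr package gives 0.1395, with power 80.3% at r = 0.14. The figure is reproduced. It concerns a variable measured in everyone and is not in question.

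**2. GWG variance in the selected 200.** Keeping the outer half of a standard normal, with cut q = 0.6745 and density φ(q) = 0.3178:

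v = 1 + qφ(q)/0.25 = 1 + 0.6745 × 0.3178/0.25 = 1.857.

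**3. Marker-GWG correlation among measured women.** r_sel = r√v / √(1 − r² + r²v).

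| Cohort r | r in the 200 | Cohort R² | R² in the 200 |
|---|---|---|---|
| 0.14 | 0.189 | 0.020 | 0.036 |
| 0.20 | 0.268 | 0.040 | 0.072 |
| 0.30 | 0.394 | 0.090 | 0.155 |

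Simulation (5,000 replicates) agrees: 0.189, 0.268 and 0.394. With no true association the simple test rejects 4.7% of the time, so its size is kept. At r = 0.14 the selected 200 give 77.8% power, against 50.9% for 200 women chosen at random. The design does its own job well; it is the effect size that does not carry over to the cohort.

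**4. Objective 4, with no true association.** Let pathogen load and inflammation be independent, each correlated −c with GWG. In the selected women:

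r_sel = (v − 1)c² / [1 + (v − 1)c²], with v − 1 = 0.857.

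For c = 0.20: 0.857 × 0.04 / (1 + 0.857 × 0.04) = 0.0343/1.0343 = 0.033.

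With unequal correlations a and b the numerator is (v − 1)ab, so the bias is zero if either is zero.

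**5. What adjustment for the high/low group would do.** Each tail has mean ±φ(q)/0.25 = ±1.271, so the GWG variance within a tail is 1.857 − 1.271² = 0.242. The partial correlation given group is (0.242 − 1)c² / [1 + (0.242 − 1)c²].

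| c | Unadjusted spurious r | Adjusted for group |
|---|---|---|
| 0.14 | +0.017 | −0.015 |
| 0.20 | +0.033 | −0.031 |
| 0.30 | +0.072 | −0.073 |
| 0.40 | +0.121 | −0.138 |

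The sign flips and the size is about the same or larger. The simulated type I error of the unadjusted test is 5.7%, 7.9% and 16.9% for c = 0.14, 0.20 and 0.30.

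**6. What does work.** In simulation of the same set-up, imputing inflammation for the unmeasured women from GWG and pathogen load gave a mean correlation of about 0.00 at every c. So did a draw of 60 women from the middle, with 140 kept at the extremes, weighted by sampling fraction.

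**The case against.** The strongest reply is that selection on a known variable is manageable. If the ranking is on GWG, every ranked woman has a GWG value, so the assays are missing at random by design. Imputation from GWG then recovers the cohort correlation, and regressing the marker on GWG within the 200 gives an unbiased slope under linearity. An analysis plan not shown here might specify this. That stands, and a reader who infers that the unmeasured middle half is beyond repair goes too far. Simple weighting cannot reach women with no chance of selection, but model-based imputation can. What remains is that this protocol fixes both the selection and the list of model inputs, and nothing in it connects the two.

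Other limits also stand:

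- The main GWG analyses in section 9.4.1 (ordination and PERMANOVA, alpha diversity, single-taxon correlations) use 16S/18S profiles planned for all women and are untouched. The integrative models complement them.
- Only the three stool markers are strictly limited to the 200. Metabolomics is a focus on them, and it serves the functional analyses rather than objective 4.
- The inflammation entry in Table 8 could include serum CRP, which is planned for all mothers, though nothing limits it to CRP.
- Section 8.1.4 ranks by WHZ. If that is not GWG, selection is not on the outcome itself and the figures above need not apply.

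A reader might also infer that marker-GWG findings would be false positives, or that objective 4 is badly compromised. The null test keeps its size, and the objective 4 bias is modest unless both factors relate clearly to GWG.

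**Conclusion.** The point holds as a mismatch between how the assays are sampled and how they are used. Extreme-group sampling is legitimate; feeding its data into cohort models and objective 4 without restriction or correction is the fault.

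Assuming normal GWG, ranking on GWG and use of measured women only, correlations with GWG are overstated by roughly a third (0.14 becomes 0.19, 0.30 becomes 0.39) and R² by up to about 1.8 times. This distorts the comparison of subset-only inputs with those measured in everyone. For objective 4 the spurious correlation is 0.02, 0.03 and 0.07 at assumed correlations with GWG of −0.14, −0.20 and −0.30, and zero if either factor is unrelated to GWG. The documents do not support reading this as a flaw in the diversity-GWG analysis or its power, or as a reason to abandon the 200 assays. It should be corrected, because the effect sizes and rankings reported would otherwise be wrong for the cohort.

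**What to change.** 1. **Section 9.4.1.** Run the cohort GWG models on variables measured in all women. Put the subset-only assays in a separate high-versus-low model within the 200, reported as an extreme-group contrast and not as cohort correlations or ranked contributions. Flag these variables in Table 8.
2. **Section 9.4.2, objective 4 and any other cohort-level estimate.** Use the known selection in one of two ways. Either multiply impute the assays from GWG and the exposure variables, which is valid under the modelled relation. Or, before assays are allocated, give part of the 200 slots (for example 60) to a random draw from the middle and weight by sampling fraction. Do not use adjustment for the high/low weight-gain group as the correction, since it reverses the bias without removing it.
3. **Section 8.1.4.** Reconcile extremes of weight gain with WHZ scores. WHZ is not defined for mothers in the protocol and is not the primary endpoint. State which variable ranks the women.

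The cost is wording in 8.1.4, 9.4.1 and 9.4.2 and one extra model run, with no extra assays. Imputation adds reliance on a model for the middle half. The random draw leaves a smaller extreme contrast (140 women instead of 200 in the example) and is possible only before allocation.

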## 2.2 BACKGROUND

### 2.2.1 UNDERNUTRITION BEFORE AND DURING PREGNANCY DRAMATICALLY IMPACTS MATERNAL HEALTH, BIRTH AND LIFE OUTCOMES

Maternal and child undernutrition, is a tremendous burden on global health. Globally, undernutrition contributes to 45% of all deaths in children under 5 years[11]. Deficiencies in macro- (e.g. proteins, lipids and carbohydrates) and/or micronutrients (e.g. minerals and vitamins) can result in stunting (low height-for-age) and/or wasting (low weight-for-height) or

thinness in adolescents and adults (low Body Mass Index – BMI). Pregnant women are particularly vulnerable due to the high nutrient demands during development of the fetus. Consequently undernutrition during pregnancy is associated with increased risk of poor birth outcomes, intra-uterine growth restriction of the fetus[12] and can result in complications that impact maternal morbidity and mortality[13-17]. In terms of perinatal outcomes, women with low BMI are at increased risk for stillbirths and neonatal deaths, preterm birth, low birth weight (LBW; <2500g) and delivering babies that are small for gestational age (SGA)[18].

Undernutrition prior to or during pregnancy may also have long term impact for the offspring (developmental origins of health and disease hypothesis)[19-21]. For example, studies of the 1944 Dutch winter famine found women exposed to famine during late gestation did not gain weight in the third trimester and had babies with reduced birth weights, who were shorter and had smaller heads and placentas than unexposed babies[22]. Mothers exposed to famine only in early -mid gestation however, gained more weight than non-exposed mothers did. The offspring of mothers with mid gestation famine exposure were lighter, shorter and had smaller heads, whereas the babies that were exposed during early gestations were heavier and longer at birth, but had higher rates of obesity[23]. **At significant risk are young women (17-24 years of age), the target demographic of this study.**

These findings broadly support the hypothesis that chronic diseases originate through adaptations made by the fetus in response to undernutrition. The long-term effects of intrauterine undernutrition, however, depend upon its timing during gestation and on the tissues and systems undergoing critical periods of development at that time.

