##### **Clinical Variables**

1. Maternal BMI, MUAC and SFT (continuous variables)
2. Maternal gestational weight gain (continuous)
3. Maternal markers of inflammation (continuous)
4. Infant sex
5. Infant morbidity and mortality
6. Infant weight, height, head circumference (continuous)
7. Infant gestational age
8. Infant birth weight, Kg (continuous)
9. Breastfeeding duration (continuous)
10. Maternal age years
11. Maternal use of antibiotics
12. Infant use of antibiotics
13. Maternal calorie and macronutrient intake
14. Maternal incidence of pathobionts
15. Infant incidence of pathobionts

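### Section 8.1.4 aims the stool assays at extremes of weight gain but ranks the women on WHZ, a score the protocol never defines, so the subset may not carry the intended contrast

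*Protocol*

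**What the plan says.** Section 8.1.4 states the selection rule twice. For calprotectin, lipocalin and claudin 15, measured in maternal stool at MV1 and MV2, the 200 women are "the two extremes of weight gain; the 100 participants with the highest and 100 participants with the lowest WHZ scores". For stool metabolomics the focus is on "the 200 participants at the two extremes of weight gain: the 100 participants with the highest and 100 participants with the lowest WHZ scores". The sample-type table in section 8 confirms 200 mothers at two visits for each of the three markers but gives no ranking variable.

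Elsewhere the protocol says:

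- **Weight gain.** Table 4 (Study Objectives) defines the primary endpoint, gestational weight gain (GWG), as "measured between the first (10-14 weeks post-conception) and second time point (30-34 weeks post conception").
- **Maternal variables.** Table 8 lists "Maternal BMI, MUAC and SFT (continuous variables") and, separately, "Maternal gestational weight gain (continuous"). Section 7.2.1.3 has height, weight, MUAC and skinfold measured in mothers.
- **Z-scores.** The only ones specified are infant outcomes: "WHO z-scores for weight, length, head circumference and MUAC during the first year".
- **Weight-for-height.** Section 2.2.1 links it to "wasting (low weight-for-height") and describes older people by "thinness in adolescents and adults (low Body Mass Index – BMI").
- **Abbreviations.** WHZ is not in the list in section 10.7.

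**The concern.** A rule for choosing extremes needs one ranking variable. Here the stated target is a change between two visits, while the ranking variable has a name that normally denotes attained size at one visit. If WHZ means a weight-for-height z-score, the protocol's own background section treats BMI, not weight-for-height, as the index for adolescents and adults.

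Two women of the same height can gain the same weight and have very different attained scores. The enrolment design adds to this, because it aims to recruit half the cohort below a BMI of 18.5 and half between 18.5 and 24.9. Ranking on attained size would largely recover the recruitment groups rather than the women who gained most and least.

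At stake is the weight-gain contrast in the assayed subset. These data meet GWG in section 9.4.1, where the network-fusion and Random Forest models relate the Table 8 variables, including the maternal stool metabolomic profile, to GWG. Once assays have been run on the wrong women, recovering the contrast means running more of them.

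**Working it through.** **1. Reading the text.** There is no stated figure to reproduce for this rule. Setting the sections side by side gives:

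| Item | Target in 8.1.4 | Ranking variable in 8.1.4 |
|---|---|---|
| Name | weight gain | WHZ |
| Defined elsewhere? | yes, Table 4 (Study Objectives): MV1 to MV2 | no |
| Maternal variable in Table 8? | yes | no |
| Visit or reference given? | both visits given | neither |

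No other section reconciles the two columns.

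**2. Inputs for sizing.** From the protocol: a cohort of 400, 100 women at each end, and BMI limits of 18.5 and 24.9. Everything else is assumed:

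- BMI stands in for weight-for-height. Enrolment BMI is normal (mean 20.5, SD 3), cut at 14, 18.5 and 24.9, and split 200/200 or 150/250.
- Height has mean 153 cm and SD 5 to 7 cm.
- GWG has mean 6 to 10 kg and SD 2 to 4 kg.
- The BMI-GWG correlation runs from -0.2 to 0.2.
- Central case: 8 kg, SD 3 kg, height SD 6 cm, correlation 0, split 200/200.

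**3. Benchmarks by formula.**

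- If the score is unrelated to gain, the expected number of true gain extremes per 100 chosen is 100 × 100/400 = 25.
- If women are ranked on gain itself, the mean gain separation between top and bottom quarters is 2 × φ(0.674)/0.25 = 2 × 0.318/0.25 = 2.54 SD.
- For a score with correlation ρ to gain (bivariate normal), the separation is about 2.54ρ. For example, 2.54 × 0.45 = 1.14 SD.

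**4. Result by reading.** Cohorts of 400 were simulated (162 input sets, 400 cohorts each). The top and bottom 100 by score were compared with the top and bottom 100 by gain, averaging the two ends.

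| WHZ read as | True gain extremes per 100, central | Range over inputs | Mean gain separation, central |
|---|---|---|---|
| score at MV1 | 24.8 | 16.8 to 33.9 | 0.0 SD |
| score at MV2 | 44.1 | 29.3 to 56.9 | 1.1 SD |
| change MV1 to MV2 | 89.6 | 78.2 to 95.0 | 2.5 SD |
| (gain itself) | 100 | – | 2.5 SD |

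A hand check of the MV2 row: BMI at MV2 is enrolment BMI plus gain/height². The SD of the second term is about 3/1.53² = 1.28. Enrolment BMI in the simulated cohorts has SD about 2.6. The correlation with gain is then about 1.28/√(2.6² + 1.28²) = 0.44, and 2.54 × 0.44 = 1.1 SD, as simulated.

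**5. Result by correlation alone** (4,000 cohorts per value):

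| Correlation of score with GWG | 0 | 0.2 | 0.45 | 0.7 | 0.9 |
|---|---|---|---|---|---|
| True gain extremes per 100 | 25.0 | 33.4 | 45.5 | 60.1 | 77.1 |
| Separation (SD) | 0.00 | 0.51 | 1.15 | 1.78 | 2.29 |

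A separate simulation counted women sent to the wrong end. At correlation 0, about 50 of the 200 true gain extremes land in the same extreme by score and about 50 in the opposite one. At 0.5 the counts are about 96 and 14.

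**The case against.** The best defence is that the intent is plain. Section 8.1.4 names weight gain twice, returns to maternal weight gain when it introduces proteomics, and GWG is the primary endpoint. WHZ is then probably a stray label. If it was meant as a change score, little is lost, since about 90 of each 100 women would be the right ones. This is a fair account of how the error arose. It does not remove it, because WHZ is the only ranking instruction given and, taken at face value, it points to an attained score.

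The magnitude rests on assumptions. That stands: the protocol gives no gain distribution and no relation between WHZ and gain. The spread from 17 to 95 per 100 shows how much depends on the reading and is not an estimate of the loss. The 0.9 column describes a stronger link than an attained score reached under these inputs, where the most was 57 per 100. An infant-score reading was not simulated; it would select on an infant outcome.

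The reach is limited, and this also stands. The diversity and taxon analyses of GWG in section 9.4.1 and the power statement in section 9.1 do not use the subset. The objective on pathogens and intestinal inflammation can be analysed in 200 women under any ranking. Section 9.4.1 sets out no explicit high-versus-low comparison within the 200. For metabolomics the wording is a focus, not a strict restriction.

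The reference and visit for a score could be left to a statistical analysis plan, so their absence alone would not be a finding. The mismatch between target and ranking variable is in the protocol itself.

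**Conclusion.** The point holds. The rule names weight gain as its target and ranks on an undefined score that is not among the maternal variables, and nothing elsewhere resolves the conflict. If WHZ is an attained score, the subset would contain roughly a quarter (MV1) to under half (MV2) of the intended women at central inputs. At MV1 that is no better than choosing at random with respect to gain. If WHZ is a change score, the loss is about one woman in ten. These figures assume 400 women with weights at both visits, BMI as a proxy, and the input ranges listed; only the direction and the dependence on the reading are firm. This should be corrected before samples are selected, but it does not threaten the cohort-wide diversity and taxon analyses of the primary endpoint.

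**What to change.** In both sentences of section 8.1.4, replace the WHZ ranking by gestational weight gain from MV1 to MV2 as defined in Table 4 (Study Objectives). If weight status was really intended, rename the target accordingly and state the score, its reference and the visit. Make the change before any stool is pulled for these assays.

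Selecting on gain means sampling on the outcome that section 9.4.1 models. This follows from the protocol's own target and is not a new problem, but associations with GWG estimated within the 200 women will look stronger than in the whole cohort and should be reported with that caveat.

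The cost is two wording corrections. The assays remain 200 women at two visits, and both weights are already scheduled.
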